5.3.3 Adjudicated Anaphylactic and Hypersensitivity Reactions

Anaphylaxis and hypersensitivity events as adjudicated positively by the anaphylaxis adjudication committee will be summarized descriptively. Listing of TEAEs of anaphylaxis and hypersensitivity and their assessment by an Independent Anaphylaxis Adjudication Committee as per the Anaphylaxis Adjudication Committee Charter will be produced by cohort.

5.3.4 Laboratory Data

Descriptive summaries of laboratory values at baseline (defined as the last assessment before or on Day 1 of OLE study), by visit, and change from baseline throughout the study will be tabulated by cohort and each treatment arm as defined in Section 5.1.1. Highest NCI CTCAE grade post-baseline will also be reported and shift tables from baseline to worst value during the study post-baseline will be presented by cohort and treatment arm as defined in Section 5.1.1.

Summaries will be analyzed for the following parameters: hematology (hemoglobin, hematocrit, platelet count, RBC count, WBC count, and differential counts [lymphocytes, eosinophils, neutrophils, monocytes, and basophils]), serum chemistries and liver function tests (sodium, potassium, chloride, bicarbonate, glucose, blood urea nitrogen, creatinine, calcium, total and direct bilirubin, total protein, albumin, alanine aminotransferase, aspartate aminotransferase, alkaline phosphatase, C-reactive protein [CRP], estimated glomerular filtration rate) and urinalysis (pH, specific gravity, glucose, protein, ketones, blood, sediment, RBCs, WBCs, casts, crystals, epithelial cells, bacteria).

Proportion of patients experiencing clinically significant changes relative to baseline will be summarized by cohort and treatment arm as appropriate for the parameters listed above.

A Hy's law analysis will be provided. The potential Hy's law quadrant is defined as ALT or AST increases above 3-fold the upper limit of normal (ULN) with concomitant total bilirubin increases above 2-fold the ULN or clinical jaundice in the absence of cholestasis or other causes of hyperbilirubinemia is considered as an indicator of severe liver injury (as defined by Hy's Law).

Visual plots (box plots or line plots) will be used to display selected laboratory parameters over time/by visit where appropriate.

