4.5.10 Laboratory, Biomarker, and Other Biological Samples

Samples for the following laboratory tests will be sent to one or several central laboratories for analysis:

- Hematology: WBC count, RBC count, hemoglobin, hematocrit, platelet count, and differential count (lymphocytes, eosinophils, neutrophils, monocytes, basophils)
- Serum chemistries and liver function tests: chloride, potassium, BUN, creatinine, albumin, AST, total bilirubin, sodium, bicarbonate (CO₂), calcium, glucose, ALK, ALT, total protein, C-reactive protein, estimated glomerular filtration rate.
- Coagulation tests: PT, PTT, INR
- Pregnancy test

All women of childbearing potential will have a serum pregnancy test at eligibility assessment visit. Urine pregnancy tests will be performed at specified subsequent visits. If a urine pregnancy test is positive, it must be confirmed by a serum pregnancy test.
- Urinalysis, including dipstick (pH, specific gravity, glucose, protein, ketones, blood) and microscopic examination (sediment, RBCs, WBCs, casts, crystals, epithelial cells, bacteria)
- SARS-CoV-2 serology testing (IgM, IgG)

In exceptional situations, upon Sponsor approval, laboratory samples may be collected off-site. The following samples will be sent to one or several central laboratories or to the Sponsor or a designee for analysis:

- Serum sample for ADA analysis
- Serum sample for tryptase and complement C3 in case of \geq Grade 2 IRRs or suspected anaphylaxis or hypersensitivity reactions
- PRM-151 plasma sample for PK analysis
 - Blood samples for determination of PRM-151 concentration will be collected from all IPF patients enrolled in Cohort A (see [Appendix 3](#)) and Cohort B patients who enrolled into the WA42293 prior to 1 June 2022 (see [Appendix 4](#)) for PK measurements
- Plasma concentration (including but not limited to predose PK samples) to measure the endogenous level of human pentraxin-2 [hPTX-2] will be analyzed from IPF patients enrolled in Cohort A and Cohort B patients who enrolled into the WA42293 prior to 1 June 2022.
- Serum and plasma samples for biomarker analysis will be collected from all IPF patients enrolled in both Cohort A (see [Appendix 3](#)) and Cohort B (see [Appendix 4](#)) for PD measurements.
- Blood PAXgene for RNA biomarker analysis will be collected from all patients with IPF enrolled in both Cohort A (see [Appendix 3](#)) and Cohort B (see [Appendix 4](#)) for PD measurements.

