Appendix 1 Schedule of Activities for Cohorts A and B (cont.)

Assessment	Eligibility assessment visit ^a	Baseline /Dosing Day 1 ^{b, c}	Dosing Day 3	Dosing Day 5	Week 4, then every 4 weeks	Week 12, then every 12 weeks	Week 24, then every 24 weeks	Treatment Discontinuation ^d	Study Completion/ Discontinuation ^d
Window	4 weeks	Loading within 8 days ^e			(±5 days)	(±5 days)	(±7 days)		
Visit number	1	2	3	4					
LABORATORY ASSESSMENTS									
Blood Tests (Hematology, Chemistry, Coagulation) ^h	x	x			x	x		x	x
SARS-CoV-2 serology ⁱ		x				x			
Urine Pregnancy test (WOCB only)	x	x	X	x	x			x	x
Urinalysis		x				x			
Serum Tryptase, Complement C3, PK, ADA sample for ≥ Grade 2 Infusion-related reactions or suspected anaphylaxis or hypersensitivity reactions ^j						x			
PK, PD, and ADA Sampling		See Appendix 3 and Appendix 4							
EFFICACY ASSESSMENTS									
Healthcare utilization for respiratory events		x	X	x	x			x	x

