Appendix 1 Schedule of Activities for Cohorts A and B (cont.)

ADA=anti-drug antibody; AE=adverse event; Discon.=discontinued; DL_{CO}=diffusing capacity for carbon monoxide; EOS=end of study; EQ-5D-5L=EuroQol 5-Dimension, 5-Level Questionnaire; HRCT=high-resolution computed tomography; IPF=idiopathic pulmonary fibrosis; IRR=infusion-related reaction; OLE=open-label extension; PCR=polymerase chain reaction; PD=pharmacodynamic; PK=pharmacokinetic; SGRQ=St. George Respiratory Questionnaire; SAE=serious adverse event; SARS-CoV-2=severe acute respiratory syndrome coronavirus 2; UCSD-SOBQ=University of California, San Diego–Shortness of Breath Questionnaire; W52=Week 52; WOCB=women of childbearing potential.

- ^a Eligibility visit can occur on the same day as dosing as long as eligibility criteria have been confirmed prior to dosing.
- ^b Patients who are rolling-over from Study WA42293 will not be required to repeat safety and efficacy assessment at Day 1 if the visit occurs within 4 weeks of Week 52.
- ^c Patients from the active treatment arm in Study WA42293 will be given placebo doses at Day 3 and Day 5.
- ^d Treatment discontinuation visit should occur 4 weeks after the last dose of study drug. Study discontinuation visit should occur, 4 weeks after the treatment discontinuation visit (8 weeks after the last dose of study drug).
- ^e To allow for flexibility around weekends, holidays, etc., the loading dose visits may occur over a time span of up to 8 days, with a minimum of 1 full calendar day between administration of doses (patients must not be dosed on consecutive days). In case one or more loading doses have been missed or delayed beyond the 8-day loading phase window, loading doses should be administered again at the next scheduled visit. No loading doses should be administered outside of the 8-day loading phase window.
- ^f On dosing days, vital signs should be completed predose (within 60 minutes prior to dosing), every 15 minutes during infusion, and 60 minutes postdose.
- ^g Full physical exam at eligibility visit and an abbreviated physical exam, thereafter.
- ^h Clinical laboratories will be assessed every 4 weeks for the first 12 weeks and every 12 weeks thereafter.

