1. INTRODUCTION

This Statistical Analysis Plan (SAP) provides details on the study design, outcome measures, and statistical analysis plan for Study WA42294 (STARSCAPE OLE). The International Nonproprietary Name (INN) zinpentraxin alfa is now the preferred name of the study drug under investigation (rather than PRM-151 or rhPTX-2); it will be used throughout this SAP wherever possible. The analyses and endpoints specified in this document supersede the analysis plan described in the study protocol.

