5.3 SAFETY ANALYSIS

The safety objective for this study is to confirm the long-term safety and tolerability of 10 mg/kg of zinpentraxin alfa administered Q4W via IV infusion plus standard of care (SOC) treatment, on the basis of the following endpoints:

- Incidence and severity of AEs, with severity determined according to the 5-point severity scale (National Cancer Institute Common Terminology Criteria for Adverse Events, Version 5.0 [NCI CTCAE, v.5.0])

- Incidence and severity of IRRs and other AEs of special interest (AESIs)
- Proportion of patients permanently discontinuing study treatment due to AEs
- Change from baseline in targeted clinical laboratory test results

Safety analyses will be based on patients from safety populations and grouped according to cohorts and the treatment groups described in Section 5.1.1.

Safety will be assessed through descriptive summary of exposure to study drug, seriousness and severity of AEs, and AESIs, changes in laboratory test results, death, discontinuation from study treatment, ECG and vital signs. These summaries will be produced for the entire study period, from the start of OLE period till the time of the snapshot or end of the study.

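### SAP 5.3.4 leaves PT, PTT and INR off its laboratory parameter list although the protocol collects them at every scheduled laboratory visit

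*SAP*

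**What the plan says.** **Collection.** Protocol 4.5.10 includes "Coagulation tests: PT, PTT, INR" among the tests sent to central laboratories. The schedule in Protocol Appendix 1 puts them in one row with the other blood panels, "Blood Tests (Hematology, Chemistry, Coagulation", and its footnote h sets the timing: "Clinical laboratories will be assessed every 4 weeks for the first 12 weeks and every 12 weeks thereafter".

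**Analysis.** SAP 5.3 gives four safety endpoints, one of which is "Change from baseline in targeted clinical laboratory test results". SAP 5.3.4 carries it out in three steps:

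- The first paragraph promises values at baseline and by visit, change from baseline and the highest post-baseline CTCAE grade for laboratory values in general. It adds that "shift tables from baseline to worst value during the study post-baseline will be presented by cohort and treatment arm".
- The second paragraph begins "Summaries will be analyzed for the following parameters: hematology" and goes on to chemistry with liver function tests and then urinalysis, item by item. It has no coagulation group.
- The third paragraph plans the proportion of patients with clinically significant change, "as appropriate for the parameters listed above".

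**Precedence.** SAP Section 1 states: "The analyses and endpoints specified in this document supersede the analysis plan described in the study protocol". SAP Appendix 1, which records changes to the protocol-planned analyses, does not mention coagulation.

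**The concern.** This is a long-term safety study, and laboratory change is one of its safety endpoints. A panel that the protocol asks for at every laboratory visit has no named place in the planned laboratory outputs. A programmer working from SAP 5.3.4 would build tables for the listed parameters and stop there. The clinical study report could then draw conclusions about laboratory safety without telling the reader that coagulation was left out of the tables.

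The protocol offers no firm fallback. Its own laboratory analysis text (Protocol 6.3.2) is general, does not name coagulation, and is superseded by the SAP.

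**Working it through.** The plan states no figure to reproduce here. The check is a comparison of two lists and a count of visits.

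**1. The lists.** Inputs are the hematology, chemistry, coagulation and urinalysis items in Protocol 4.5.10 and the items in SAP 5.3.4.

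| Group | Protocol 4.5.10 | SAP 5.3.4 |
|---|---|---|
| Hematology | 10 | 10 |
| Chemistry and liver function | 16 | 17 |
| Coagulation | 3 | 0 |
| Urinalysis | 13 | 13 |
| Total | 42 | 40 |

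In the protocol but not in the SAP: PT, PTT and INR, and nothing else. In the SAP but not in the protocol: direct bilirubin; Protocol 4.5.10 lists only total bilirubin. Check: 42 − 3 + 1 = 40. With the three tests added, the SAP list has 43 items and covers all 42 in the protocol.

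**2. Which outputs are affected.** The summary of clinically significant change refers back to the list, so the exclusion there is express. The by-visit, change-from-baseline, grade and shift outputs are promised one paragraph earlier for laboratory values generally. For these the exclusion is an inference: the list that follows most naturally says which parameters that paragraph covers. Where the SAP wants an open list it says so, in 5.3.2 and 5.6.2; it does not do so in 5.3.4.

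**3. Whether another section picks coagulation up.** None does. In the SAP the abbreviation PT stands for Preferred Term. Other items in the same Protocol 4.5.10 list do have a place elsewhere: SARS-CoV-2 serology in SAP 5.6.8, and a pregnancy listing in SAP 5.3.2.

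**4. Scheduled panels per treated patient.** These are counted from Day 1 under footnote h of Protocol Appendix 1, without eligibility, discontinuation or completion visits.

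- Through Week 52: Day 1 and Weeks 4, 8, 12, 24, 36 and 48, which is 7 panels.
- Through Week 104: add Weeks 60, 72, 84 and 96, so 7 + 4 = 11 panels.
- Cohort B patients who roll over within 4 weeks of the parent study's Week 52 visit need not repeat the Day 1 safety assessments (footnote b), and SAP 5.1 uses the parent values instead. For them the new panels through Week 52 are 7 − 1 = 6.

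**The case against.** Four points on the other side have weight.

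- **The opening of SAP 5.3.4 is general.** It promises summaries, grades and shifts without restriction, and the list sentence mentions neither grades nor shifts. This stands: only the clinically significant change summary is expressly limited. It leaves the text ambiguous for the other outputs, which is itself a reason to add the three names.
- **Abnormal results still have a route into the report.** A reader might infer that a coagulation problem would never be noticed. The documents do not support that. Protocol 5.4.5.5 makes investigators review all laboratory findings and report as an adverse event any that is symptomatic, changes treatment, leads to an intervention or a change in concomitant therapy, or is judged clinically significant. Protocol 4.5 makes dosing conditional on acceptable values from the previous visit, and SAP 5.3.2 tabulates the adverse events. This route depends on case-by-case judgment, however, and does not show drift or shift across a cohort.
- **The endpoint covers targeted tests only.** Protocol 6.3.2 likewise speaks of relevant and selected tests, so neither document promises to tabulate everything collected. A deliberate exclusion is possible. But the SAP repeats every other routine item, down to casts and crystals, and gives no reason for leaving out these three.
- **No coagulation risk is named for this drug.** Protocol 5.1 and the list of adverse events of special interest contain no bleeding or clotting event. This stands, and it limits the consequence: the point concerns complete reporting, not a suspected signal.

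A reader might also multiply panels by patients to get a total. The documents do not give the number treated. The 600–700 enrolment figure includes Cohort C, which has no laboratory assessments, and attrition is unknown.

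**Conclusion.** The gap is real and limited. PT, PTT and INR are the only routine laboratory parameters that the protocol collects and the SAP does not list. They are expressly outside one planned output, the summary of clinically significant change. On the natural reading they are outside the by-visit, change-from-baseline, grade and shift summaries as well. On that reading, an abnormal value enters the report only through adverse event reporting.

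The size is six to seven scheduled panels per treated patient through Week 52. This assumes that the patient stays on schedule that long; six applies to Cohort B patients whose Day 1 values carry over. The documents do not say whether the parent study's Week 52 visit includes coagulation. The effect is confined to descriptive safety reporting. No efficacy estimate or planned test is touched.

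**What to change.** Add a coagulation group (PT, PTT, INR) to the parameter list in SAP 5.3.4. The three tests should get the same by-visit, change-from-baseline, shift and clinically significant change outputs as the other panels, by cohort and treatment group, with highest CTCAE grade where the test is gradable. If the omission was intended, SAP Appendix 1 should say so and give the reason.

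As a minor reconciliation in the same section, state where direct bilirubin comes from or remove it.

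The cost is a line of SAP text and a few rows in tables already planned. The tests are already scheduled, so no new data collection or protocol change is needed.

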5.3.5 Vital Signs

Values, along with change from baseline, will be summarized using descriptive statistics for each vital sign parameter.

Summary statistics on absolute values and their change from baseline for all observed vital signs (respiratory rate, pulse rate, systolic and diastolic blood pressure while the patient is in a seated position, oxygen saturations, and temperature) will be presented over time by cohort and treatment group as defined in Section 5.1.1. Baseline is defined as the last assessment prior to treatment on Day 1 of OLE study.

5.3.6 ECGs

A shift table for patients with ECGs clinically significant abnormalities (from baseline to worst condition after baseline) will be produced.

5.3.7 Other Safety Endpoints

Summaries of safety data by ADA status will be provided as appropriate. See Section 5.6.5 for more details on ADA status.

5.4 EFFICACY ANALYSIS

All efficacy analyses will be performed on the FAS population for cohort A and B, unless otherwise specified. Efficacy analysis will be presented over time by cohort and treatment group as defined in Section 5.1.1.

Efficacy will be assessed by annual rate of change in FVC (mL), 6MWD, FVC% predicted, and carbon monoxide diffusing capacity (DL_{CO}), time to disease progression, and survival as measured by all-cause mortality, IPF-related mortality and respiratory-related mortality.

All efficacy parameters will be summarized descriptively, and as all patients will be receiving zinpentraxin alfa, there will be no hypothesis testing between treatment groups defined for cohort B. Wherever possible 95% confidence intervals will be reported for estimates.

The annual rate of change in FVC (mL), 6MWD, FVC% predicted, and DL_{CO} will be calculated using the slope from a linear mixed effect model with random intercept

(subject) and random slope (time), using measurements collected at each time point in this study. The model will include patient gender, age, and height at baseline, study day of the visit and strata (region and concurrent use of IPF treatment). When analyzing data from Cohort B, treatment group and treatment by time interaction will be added to the model as covariates.

With respect to handling of missing data in the assessment of spirometry data (FVC [mL], FVC% predicted, and DL_{CO}), all measurements that meet the minimal level of quality (except those recorded after lung transplantation) will be used. For the purpose of determining the annual rate of change estimates, a hypothetical strategy will be utilized where values will be implicitly imputed from the model for the majority of data impacted by intercurrent events with the exception of death due to IPF.

For death, a hypothetical strategy will be utilized where after death assessments will be implicitly imputed using linear mixed-effect model. See [Table 3](#) for details.

Table 3 Analysis Strategy for Intercurrent Events for FVC, 6MWD, FVC% Predicted, and DL_{CO}

Intercurrent Event (ICE)		Analysis Strategy
Any change to treatment	Permanent study drug discontinuation	Hypothetical strategy
		Implicit imputation using linear mixed-effect model
Any change in standard of care (SOC), with pirfenidone or nintedanib therapy	SOC started during study	Treatment policy
	Change in dose of SOC	All measurements post ICE analyzed
	SOC discontinued	
	SOC switch (from pirfenidone to nintedanib or vice-versa)	
Other concomitant treatment	Use of prohibited concurrent medication (Protocol Section 4.4.2)	Treatment Policy
		All measurements post ICE analyzed
Terminal events	Death	Hypothetical strategy
		Assessments following death will be implicitly imputed using linear mixed-effect model
	Lung transplantation	Hypothetical strategy
		Measurements collected after lung transplantation excluded from the analysis
	Implicit imputation using linear mixed-effect model	
	Hospitalization for COVID-19	Treatment Policy strategy
		All measurements post ICE analyzed

COVID-19=Coronavirus Disease 2019; ICE = intercurrent event; SOC = standard of care.

In the hypothetical strategy, the model implicitly imputes missing data based on an individual's estimated rate of worsening of lung function prior to study discontinuation (i.e., assuming missing at random).

In addition, summaries using all observed data will be performed.

Summary statistics (number of patients, mean, standard deviation, median, minimum, maximum) on absolute values and their change from baseline for several observed efficacy evaluations (FVC [mL], 6MWD, FVC% predicted, and DL_{CO}) will be presented over time by cohort and treatment group as defined in Section 5.1.1. Baseline is defined as any last assessment prior to treatment on Day 1 of OLE study.

5.4.1 Time-to-Event Endpoints

The time-to-event secondary endpoints are listed below:

- Time to disease progression, defined as time to first occurrence of $\geq 10\%$ absolute decline in % predicted FVC, $\geq 15\%$ relative decline in 6MWD, or death
- Survival, as measured by all-cause mortality, IPF-related mortality and respiratory-related mortality

Descriptive statistics for the frequency of each type of event will be provided. The Kaplan-Meier plot, median time to event, and their 95% CIs.

Time-to-event will be measured in reference to Baseline Day 1 of OLE study through the end of study or the time of the data-cut, whichever occurs first. For time to disease progression and survival (as measured by all-cause mortality, IPF-related mortality and respiratory-related mortality), patients without an event will be censored at the last clinic assessment.

The strategy for the time-to-event endpoints is summarized below in [Table 4](#).

Table 4 Strategy for Addressing Intercurrent Events: Time-to-Event Endpoints

Endpoint	Intercurrent Events and Strategy
Time to disease progression, defined as time to first occurrence of $\geq 10\%$ absolute decline in % predicted FVC, $\geq 15\%$ relative decline in 6MWD, or death	Any patients who undergo lung transplantation will be censored at the date of the transplant (hypothetical strategy) Any patients who withdraw from treatment will be censored at the date of last disease progression assessment, i.e., % predicted FVC and 6MWD (hypothetical strategy)
Survival, as measured by all-cause mortality, IPF-related mortality and respiratory-related mortality	Any patients who undergo lung transplantation will be censored at the date of the transplantation (hypothetical strategy) Any patients who withdraw from treatment will be censored at the date of withdrawal (hypothetical strategy)

6MWD = 6-minute walk distance; FVC = forced vital capacity; IPF = idiopathic pulmonary fibrosis.

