1.2.2.4 Deaths due to Respiratory Causes

All deaths occurring during the study must be recorded. The event or condition that caused or contributed to the fatal outcome should be recorded as a single medical concept on the Adverse Event electronic Case Report Form (eCRF).

All investigator-reported deaths that occur in Cohorts A or B will be assessed by an independent Adjudication Committee to determine whether each death was related to IPF, another respiratory cause or an alternative (non-respiratory and non-IPF) cause. Deaths occurring in Cohort C will not be adjudicated.

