5.1 GENERAL CONSIDERATIONS

All analyses will be reported separated by cohort.

Patients who are rolling-over from Study WA42293 will not be required to repeat safety and efficacy assessment at Day 1 if the visit occurs within 4 weeks of Week 52: in these cases, assessments from Week 52 of Study WA42293 will be used as Day 1 assessments.

The safety analyses will be performed on the safety-evaluable population, unless otherwise specified. Safety will be assessed through descriptive summaries of exposure to zinpentraxin alfa study drug, AEs, and laboratory test results.

All efficacy analyses will be performed on the full analysis set (FAS) population, unless otherwise specified. Patients in Cohort B will be analyzed according to the treatment assigned at randomization by interactive voice/Web-based response system (IxRS) in the parent study.

Cohort B collected data will not be analyzed before unblinding of the code of the treatment received by the patient during the parent Study WA42293. The main analysis will take place at the time of unblinding and main analysis of the parent Study WA42293. If unblinding of the Study WA42293 will occur earlier than the 52-week visit of the last patient enrolled in Cohort B, additional efficacy analysis will be implemented at the time when all patients in Cohort B had their 52-week visit or withdrew from the study, whichever is earlier.

Additional safety update analyses maybe conducted as required by Health Authorities. The final analysis will take place after the last patient last visit (LPLV).

All outputs relevant to Cohort C will have a footnote specifying that most part of the patients has contributed also to Cohort A and Cohort B.

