 - Cases of potential drug-induced liver injury that include an elevated alanine aminotransferase (ALT) or aspartate aminotransferase (AST) in combination with either an elevated bilirubin or clinical jaundice, as defined by Hy's Law (see Protocol Section 5.4.)
 - Suspected transmission of an infectious agent by the study drug, as defined in Protocol Section 5.3.
 - Suspected IRR with NCI CTCAE Grade ≥ 2
 - Suspected anaphylactic or hypersensitivity reactions (all grades)
 - Acute or suspected exacerbation of IPF (all grades)

- Common AEs, i.e., those occurring in at least 5% of patients
- Suspected IRR (all grades)

Summaries of safety data by baseline concurrent anti-fibrotic therapy will be provided as appropriate.

Deaths and causes of death will be summarized and a listing of patients who died during the study will be provided.

Summaries of confirmed or suspected Coronavirus Disease 2019 (COVID-19) AEs and AEs associated with COVID-19 will also be provided.

A listing of all pregnancies will be presented.

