5.5.1 Time-to-Event Exploratory Endpoints

The time-to-event exploratory endpoints are listed below:

- Time to first respiratory-related hospitalizations (defined as non-elective hospitalizations due to any respiratory cause, including acute exacerbations of IPF, or suspected acute exacerbations of IPF, as determined by Adjudication Committee)
- Time to first acute exacerbation of IPF, or suspected acute exacerbation of IPF, as determined by Adjudication Committee

Time-to-event will be measured in reference to baseline Day 1 of OLE study through the end of study or the time of the data-cut, whichever occurs first. For time to first respiratory-related hospitalizations and time to first acute exacerbation of IPF, patients not experiencing an event will be censored at the earliest of the last known alive day.

The strategy for the time-to-event endpoints is summarized below in [Table 5](#).

Table 5 Strategy for Addressing Intercurrent Events: Time-to-Event Exploratory Endpoints

Endpoint	Intercurrent Events and Strategy
Time to first respiratory-related hospitalizations (defined as non-elective hospitalizations due to any respiratory cause, including acute exacerbations of IPF, or suspected acute exacerbations of IPF, as determined by Adjudication Committee)	
Deaths due to IPF or other respiratory causes will be treated as disease progression and counted as event of interest (composite strategy)
 
Deaths due to other causes will be censored
 
Any patients who undergo lung transplantation will be censored at the date of the transplantation (hypothetical strategy)
 
Any patients who withdraw from treatment will be censored at the date of withdrawal (hypothetical strategy)

Time to first acute exacerbation of IPF, or suspected acute exacerbation of IPF, as determined by Adjudication Committee	
Deaths due to IPF will be treated as disease progression and counted as event of interest (composite strategy)
 
Deaths due to non-IPF causes will be censored
 
Any patients who undergo lung transplantation will be censored at the date of the transplantation (hypothetical strategy)
 
Any patient who withdraws from treatment will be censored at the date of withdrawal (hypothetical strategy)

IPF = idiopathic pulmonary fibrosis.

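### SAP 5.4.1 plans Kaplan-Meier for IPF-related and respiratory-related mortality and by implication censors other-cause deaths, which overstates the risk of dying from the named cause

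*SAP*

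**What the plan says.** SAP 5.4.1 has two entries in its list of time-to-event endpoints. The first is time to disease progression. The second is survival, measured by all-cause, IPF-related and respiratory-related mortality. The analysis follows in a fragment without a verb: "The Kaplan-Meier plot, median time to event, and their 95% CIs". The next paragraph names all three mortality endpoints and says that "patients without an event will be censored at the last clinic assessment".

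For these endpoints Table 4 lists only two intercurrent events, lung transplantation and withdrawal from treatment. Both lead to censoring and both are labelled hypothetical. Death from a cause other than the one counted does not appear.

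Table 5 in SAP 5.5.1 does address such deaths. For time to first respiratory hospitalization, "Deaths due to other causes" are censored. For time to first exacerbation, "Deaths due to non-IPF causes" are censored. Respiratory or IPF deaths (hospitalization) and IPF deaths (exacerbation) count as events there. SAP 5.5.1 names no estimator, but protocol 6.5 names Kaplan-Meier for these two endpoints.

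Protocol 6.4 names Kaplan-Meier only for disease progression and time to death. SAP section 1 says that the SAP supersedes the protocol's analysis plan. Neither document mentions competing risks or cumulative incidence.

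**The concern.** Kaplan-Meier treats a censored patient as someone who could still have the event later, at the same rate as those who remain under observation. A patient who has died of another cause cannot. Censoring that patient redistributes the probability to those still at risk, so the curve describes a setting in which nobody dies of anything else. It is not the chance that a patient in this study dies of IPF.

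IPF-related and respiratory-related mortality are named efficacy endpoints in protocol 2.2 and in SAP Table 1. In a study without tests the estimates are the result, and these curves and medians would naturally be read as risks of dying from that cause. The SAP also plans event frequencies in 5.4.1, and 5.3.2 says "Deaths and causes of death will be summarized". Those summaries show that other-cause deaths occur, but they ignore follow-up time and do not replace a correct curve.

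**Working it through.** The plan gives no figure to reproduce, so the check has a reading step and an illustration of size.

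**Reading.** Someone who dies of a non-IPF cause has no IPF-related event. The only SAP rule that fits this patient for IPF-related mortality is the one for patients without an event, which is censoring. Table 4 offers no alternative.

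**Direction.** Let h1 be the hazard of the cause of interest, with S1 and S2 the survival functions built from the cause-specific and other-cause hazards. Then 1-KM(t) is the integral of S1·h1, and the cumulative incidence (CIF) is the integral of S1·S2·h1. Because S2 ≤ 1, 1-KM is never below the CIF, whatever the shape of the hazards.

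**Size: inputs.** These are background figures in the protocol, not design inputs.
- 5-year survival S5 of 20% to 40% (protocol 1.1).
- IPF share of deaths p = 60% (protocol 3.3.3). Section 1.1 words the 60% differently, so 50% to 70% is also shown.
- Constant hazards (assumed).

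**Formulas.** All-cause hazard h = -ln(S5)/5. 1-KM(t) = 1 - exp(-p·h·t). CIF(t) = p·(1 - exp(-h·t)).

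S5 = 0.2 gives h = 0.3219, and S5 = 0.4 gives h = 0.1833. With p = 0.6:

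| Years | S5 = 0.2: 1-KM v CIF (%) | Excess (points) | S5 = 0.4: 1-KM v CIF (%) | Excess (points) |
|---|---|---|---|---|
| 1 | 17.56 v 16.51 | 1.05 | 10.41 v 10.05 | 0.37 |
| 2 | 32.04 v 28.48 | 3.56 | 19.74 v 18.41 | 1.33 |
| 3 | 43.98 v 37.16 | 6.82 | 28.10 v 25.38 | 2.72 |
| 5 | 61.93 v 48.00 | 13.93 | 42.29 v 36.00 | 6.29 |

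**Coherence check** (S5 = 0.2, 5 years). 1-KM for other-cause death is 1 - exp(-0.4 × 0.3219 × 5) = 47.5%. Added to 61.9% for IPF death, this makes 109.4%, while all-cause mortality is 80%. The two CIFs, 48% and 32%, sum to 80%.

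**Medians.** The Kaplan-Meier median is ln2/(p·h). The CIF reaches 50% at -ln(1 - 0.5/p)/h. With p = 0.6 these are 3.59 v 5.57 years (S5 = 0.2) and 6.30 v 9.78 years (S5 = 0.4).

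**Sensitivity of the excess (points).**
- IPF share 50% to 70%: 0.3 to 1.1 at 1 year, 2.3 to 7.3 at 3 years, 5.3 to 15.3 at 5 years.
- Respiratory-related mortality, assumed share 70% to 90%: 0.1 to 0.9, 1.0 to 5.8 and 2.2 to 11.6 at the same times.
- Assumed annual mortality of 5% and 10%, p = 0.6: 0.03 and 0.13 at 1 year, 0.26 and 1.02 at 3 years, 0.69 and 2.53 at 5 years.
- Median survival of 2 to 5 years (protocol 3.3.3), h = ln2/median, p = 0.6: 4.0 to 0.8 at 2 years and 15.3 to 4.0 at 5 years.

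A simulation of 200,000 patients agrees with the closed form. For a 2-year median it gives 64.8% v 49.4% at 5 years, against 64.6% v 49.4%. Moving the censoring back to the last 4-weekly visit changes 1-KM by about 0.2 points or less.

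The documents give no event rates for the Table 5 endpoints, so no figure is offered for them.

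**The case against.** - **The reading is inferred.** The SAP never says outright that other-cause deaths are censored for the two mortality endpoints, and the Kaplan-Meier fragment does not name them. That is true. But the fragment directly follows the list that contains them, the censoring sentence does name them, and Table 5 shows the same choice made explicitly.
- **The consequence is limited.** There are no tests, all-cause mortality is reported, and deaths will be tabulated by cause. This stands, and it caps the importance of the point.
- **The size may be smaller.** With a 5-year median survival the excess is 0.2 points at 1 year and 4.0 at 5 years, below the lower ends of the main illustration. This also stands. The case lies between the 5% to 10% annual mortality scenario and the main one, and the documents give no on-treatment mortality that would settle it.
- **Aalen-Johansen does not repair censoring at treatment withdrawal.** Correct. That is a separate issue which may bias in the other direction, so no net direction is claimed here.
- **Adjudication is incomplete.** Patients who stop treatment move to Cohort C, where deaths are not adjudicated. This matters only if censoring at withdrawal is lifted.
- **Table 5 is explicit and exploratory.** Yes, and its composite events leave fewer deaths to compete. The same defect remains for those that do.

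**Conclusion.** The concern holds. As written, the plan yields curves and medians for IPF-related and respiratory-related mortality that overstate the risk of dying from that cause, through this component of bias. The amount depends on mortality, on the share of other-cause deaths and on follow-up time. Under constant hazards it ranges from a negligible 0.03 points (1 year, 5% annual mortality) to about 15 points (5 years, 2-year median survival). Early on it is likely to be small, and "The main analysis will take place at the time of unblinding and main analysis of the parent Study WA42293". It matters mostly at the final analysis after the last patient's last visit, expected by 31 December 2028. All-cause mortality and time to progression, which count every death, are not affected, nor is any test or sample size. The change should be made, but the study's conclusions do not hinge on it.

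**What to change.** - In SAP 5.4.1, estimate IPF-related and respiratory-related mortality by the Aalen-Johansen cumulative incidence function with 95% confidence intervals. Treat other-cause death as a competing event at the date of death.
- Add a row for other-cause death to Table 4. State how lung transplantation and treatment withdrawal are handled in the same analysis.
- Report cumulative incidence at fixed times, for example 1, 2 and 3 years.
- In SAP 5.5.1, use the same estimator for the two Table 5 endpoints and keep their composite events.
- Keep Kaplan-Meier for all-cause mortality and time to progression.
- If Kaplan-Meier is nevertheless retained for a cause-specific endpoint, label it as a hypothetical quantity and not as a risk.

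The cost is SAP wording and a standard procedure. No new data are needed while censoring at withdrawal stands, because deaths in Cohorts A and B are already adjudicated "to determine whether each death was related to IPF, another respiratory cause or an alternative (non-respiratory and non-IPF) cause". If that censoring were lifted, the lack of adjudication in Cohort C would have to be addressed. One drawback is that a median time to cause-specific death may not be reached, which is why the fixed-time estimates are needed.
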